## **2.7.2 Qualitative component**

The qualitative component will constitute individual in-depth interviews (IDIs) with married AGYW and husbands of AGYW (Nigeria alone), focus group discussions (FGDs) with married AGYW and key informant interviews (KIs) with health providers and mobilizers. Participants for this component will have been purposely sampled with the assistance of the program team and then approached and the primary contact details for those who express interest to participate gathered and shared with the research team. No secondary contact details will be collected. Only AGYW, husbands and health workers and mobilizers working in the intervention areas will be eligible for this component – comparison areas will be excluded.

A few days prior to the date of the IDI, FGD or KII, potential participants will be contacted and asked if they are still interested to participate in the study (**using Appendix G, H or I**). Individuals who are still interested will be invited to congregate in a specific venue (a health facility or a community social hall) at a specific date and time. This component will be executed at the same time and in concurrency (there will be FGDs, KIIs and IDIs scheduled on the same day) and there will be limited flexibility on where data collection could occur. This will reduce the costs related to the logistics of moving the qualitative team between multiple venues. On the date of the IDI, FGD or KII prior to their participation, individual written consent will be obtained. Selected potential participants who decline to participate at this point will be replaced. For the FGDs, KIIs and IDIs, the sessions will be conducted in quiet secluded venues. The sessions will be recorded (voice only) using digital voice recorders and transcribed verbatim subsequently. Potential participants who decline to have their sessions audio recorded at the time of consenting will not be allowed to participate.

## **2.8 DATA MANAGEMENT**

### **2.8.1 Quantitative data**

The quantitative data will be gathered using a Computer Assisted Personal Interview (CAPI) approach. SFH and PSI Ethiopia will avail institutional tablets to VKM and Deep Dive Research and Consulting PLC for collecting quantitative data at all phases of the evaluation. A data entry template shall be developed through Survey CTO software. The survey tool shall be designed in English and local languages of the study regions with a drag and drop user interface. Thus, data collection as well as data entry shall be accomplished at the same time, accurately and timely. The data will be transferred (exported) into STATA software. Before analysis, further data check-up will be made. Preliminary analysis such as skewedness and kurtosis tests will be conducted to check and confirm that the data set is free from outliers. Appropriate statistical measurements will also be made to correct such data.

Data collection tools will be rigorously pretested before they are used for actual data collection. This will involve conducting mock interviews by the core study team (investigators) to detect any errors and by the enumerators and the field supervisors during the training prior to data collection. Because enumerators and supervisors will be native speakers of the local languages, this pre-testing will enable the study to identify issues that might have emerged during the translation of the tools. By the end of the enumerator training, each enumerator will be expected to have conducted a minimum of five mock interviews. All the feedback gathered through the pre-testing process will be used to make minor tweaks (such as the framing of questions) to the tools before they are ready for fielding to actual participants. Should be any substantive changes such as dropping or adding new questions, an amendment submission will be made to the REBs. Pre-testing will also enable checks to the electronic version of the tool and check for any skip logic errors.

When building the tool in Survey CTO software automated live data checks, extensive validations and cross-checks will be programmed. This will reduce errors and inaccuracies during the personal interview. Data shall be uploaded to the cloud daily, to enable the PI and data manager carry-out a range of consistency checks daily. Global positioning system (GPS) coordinates will be collected for all survey participants (as part of the study record) and will be used to validate the location of enumerators and specifically where data has been collected. It will also be used to uncover unusual patterns of participant recruitment. Furthermore, the GPS data will also be used to track if there are differences in the locations where study participants are interviewed from the initial and follow-up interviews. GPS data will be stripped out of the dataset during data cleaning and de-identification. The data will be synchronized with a web-based server intermittently. The mobile devices will be password protected and handled only by the enumerators. All phone call logs from the phones used to recruit and schedule follow-ups with participants will be deleted immediately after each survey phase is completed, under the supervision of field supervisors. Data collection will only be performed using institutionally-owned tablets (owned by SFH or PSI-Ethiopia).

### **2.8.2 Qualitative data**

The IDIs, FGDs and KIIs will be recorded using digital voice recorders with consent from study participants. Audio files will be stored in a password-protected file in the PSI SharePoint until transcription is complete. Audio files will be destroyed after transcription is complete. When collecting data, we will ensure that the data collected are of high quality so that they can be reliably used as the basis to make sound decisions.

### **2.8.3 Quality assurance**

The following data quality assurance measures shall be taken throughout the evaluation implementation to ensure the collection of high-quality data. The field team members from VKM and Deep Dive Research and Consulting PLC will be provided with a three-days' intensive training to undertake the field data collection effectively and efficiently. All data collection tools, recruitment scripts and consent forms will be translated to local language (Affan Oromo, Sidamayya and Amharic languages in Ethiopia and Hausa for Nigeria) and back translated to English.

On site supportive supervision, which includes over-the-shoulder observation of enumerators will be carried out in every study area by field supervisors from VKM and Deep Dive Research and Consulting PLC shadowed by the Co-Investigators from PSI Ethiopia and SFH. The evaluation field supervisors shall conduct back-check interviews revisiting about 10% of conducted interviews, to observe and make sure whether enumerators were properly administering interviews, as per the evaluation protocols. Information about the back-checks has been provided as part of consenting procedures but it will be voluntary. It will be guided by a back-check script (Appendix T). Back checks will only be conducted among AGYW who have been reached through their primary contact details on phone, those reached in-person or through other people's numbers will be excluded. By the end of each field day, a debriefing session will be held. The sessions will be led by the field supervisors and will give an opportunity for enumerators to reflect their observations, challenges

encountered and other issues. After each debriefing, strategies and mechanisms will be disseminated to the entire team to avoid duplication of similar challenges and issues.

For Ethiopia to address the mishap resulting to over sampling non-pregnant girls, the following measures will be executed. We will (1) develop a daily recruitment log, illustrating the proportion of participants who are pregnant versus those who are not, at the site level and aggregating these upwards to the regional level (2) daily monitoring of the records submitted to Survey CTO using the Monitor menu in the software, (3) manual tallying of recruited participants in the Amhara region where internet issues were being experienced and therefore the electronic monitoring was impossible, (4) allocating the sample quotas to enumerators so that when they reach the allocated number of non-pregnant girls, they stop recruiting them and just focus on recruiting pregnant girls alone and (5) moving recruitment to an adjacent kebele if the sample numbers for were not reached in one kebele but paying closer attention to the study group most affected by the low recruitment numbers, (6) more intimate engagement with Deep Dive through a progress review meeting twice weekly so that any challenges are discovered and action implemented immediately.

## **2.9 DATA ANALYSIS**

### **2.9.1 Quantitative analysis**

Quantitative data will be analyzed using univariate, bivariate and multivariate analysis to address the objectives of the study under the stewardship of PSI. Between group t-tests and chi-square tests of comparison will be conducted at recruitment phase to identify any areas in which there are statistically significant differences between the intervention and comparison groups and also compare within individual differences between the initial phase and follow-up phases. The analysis for the outcomes of interest will follow a difference-in-difference design (DiD). For the primary outcome, a two-group repeated measures design with a binary response and with two measurements for each subject will be used to test whether there is a difference in group slopes. The comparison will be made using a Wald Z-test using GEE methods. The repeated measurements of each subject will be made at 2 times and using an autoregressive correlation structure (AR1). At the follow-ups and within reason, any statistically significant differences between the intervention and comparison groups will be attributed to the intervention. Generalized linear mixed affects models will be employed to control for confounding correcting for individual and cluster-level standard errors.

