For the implementation science component, we will employ eight (8) focus group discussions (FGDs) and 48 semi-structured in-depth interviews (IDIs) with AGYW, 10 IDIs with husbands (Nigeria only) and 35 key informant interviews (KII) with providers and mobilizers (female mentors, ANC providers and male interpersonal communication agents- MPICAs). The participants will be shared equally between Ethiopia and Nigeria except MIPCAAs who will only be from Nigeria. All the FGDs, IDIs and KII will be conducted with individuals who have been involved in the MNCH components. The qualitative impact protocol (QuIP) approach will guide the execution of this component. It will be conducted mid-way through the implementation of the intervention. Participant recruitment will be conducted using recruitment scripts after obtaining oral consent and the administration of a set of screening questions to assess eligibility. Full consenting procedures will be conducted, and written consent obtained prior to involvement in any of the evaluation components. A structured questionnaire will be used to gather quantitative data from the survey using a Computer Assisted Personal Interview (CAPI) approach. Furthermore, FGD, IDI and KII facilitation guides will be used to gather qualitative data and all sessions will be audio-recorded. Audio records will be transcribed verbatim and translated. Data will be collected by trained enumerators certified to conduct human subjects' research through Viable Knowledge Masters (VKM) in Nigeria and Deep Dive Research and Consulting Inc who have been contracted as local research partners (working as consultants) in Nigeria and Ethiopia respectively.

Analysis of quantitative data will follow a repeated measures approach using Wald Z-test employing generalized estimating equations. The repeated measurements of each subject will be made at two times and using an autoregressive correlation structure. Between group t-tests and chi-square tests of comparison will be conducted to identify secondary outcomes which show statistically significant differences between the intervention and comparison groups. The qualitative data transcripts will be rigorously analyzed using NVivo or Dedoose. Open-coding and closed-coding will be utilized to identify themes in the qualitative data. Claim statements attributing change to key intervention drivers will be drawn from narrative stories of program beneficiaries guided by the intervention's theory of change.

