## **2.6 SAMPLE SIZE ESTIMATION AND SAMPLING PROCEDURES**

The sample size for the quantitative survey is estimated using a two-sided Wald Z-test using GEE methods, accounting for repeated measures and clustering within groups and assumes no change of the estimate for the primary outcome for the study within the comparison group. The primary outcome will be a binary measure, which documents whether the AGYW has met criteria for 'comprehensive' knowledge of what is needed at conception to attain a healthy pregnancy. It will be estimated from a composite measure made from a combination of questions assessing AGYW about their knowledge about behaviors (proper nutrition, screening tests and treatment for HIV and sexually transmitted infections, use of prenatal vitamins, and avoidance of harmful substances). These questions are curated from a systematic review conducted in Ethiopia on the knowledge of preconceptual care and which is also relevant for Nigeria(Ayele et al., 2021). This study established a pooled estimate of good knowledge of preconceptual care of 30.9%. In our study, an AGYW will be comprehensively knowledgeable if she responds to the affirmative to all the questions. The questions will be fielded at the time of recruitment and repeated 3 months later.

To detect an effect size of 10% (between recruitment and 3 months later assuming no change in the comparison group), with a power of 80% at the 95% confidence level (two-sided), we would need a sample size of 991 participants in each country equally split between the comparison and intervention group. This assumes an adjustment of 10% for non-response and a design effect of 1.2. Appendix R (page 57) summarizes sample sizes with different scenarios of estimated effect sizes. We adjust this sample upwards by 10% to account for attrition that might occur between recruitment and the follow-up after 3 months to arrive at a sample size of 1,090 which when split between the groups would be 545 AGYW. Cumulatively for Nigeria and Ethiopia, the final sample size would entail 2,180 participants. This sample is increased by 240 to 2,420 to account for recruitment adjustments for Ethiopia.

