A two-group repeated measures design with a binary response and with 2 measurements for each subject will be used to test whether there is a difference in group slopes. The comparison will be made using a Wald Z-test using GEE methods. The repeated measurements of each subject will be made at 2 times and using an autoregressive correlation structure (AR1). The initial proportions  $P1(0)$  and  $P2(0)$  are estimated at 0.3 based on estimates in the literature (preconception care knowledge).  $P2(1)$  proportion assumes no change in the primary outcome over the course of the intervention. Estimates are adjusted by 10% missing/non-response rate and a design effect of 1.2 to account for within community or group clustering.

Table 2 shows estimated total sample sizes for the primary and secondary target populations included in this study.

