## **2.11 LIMITATIONS**

This evaluation will have its own limitations. First, the intervention outcomes will be measured between participants who receive the revamped MMA and Smart Start interventions against the current package of SRH interventions. So far, it is possible that the current package could be delivering some elements of maternal and child health (especially in Nigeria). An ideal comparator would have been participants receiving services through routine government facilities that are not supported at all by the A360 project. Unfortunately, the recruitment to the evaluation might not be feasible. Second, this study will only recruit AGYW from catchments of health facilities (as clusters). The clustering of effects within AGYW from specific facility catchments cannot be controlled. Third, this evaluation will rely on self-reports to collect data on the primary and secondary outcomes. Using self-reports is amenable to social desirability biases. Although we plan to meticulously order the survey questions so that sensitive items are only fielded when the rapport between the enumerator and the participant has been formed. Furthermore, we will triangulate the two main sources of data for this study when processing the findings and complement these with comparison of routinely collected program data before we can interpret the data and draw conclusions. Fourth, the qualitative component will only involve AGYW, husbands and health workers and mobilisers who own a functional primary mobile number. This excludes individuals without access to a mobile number and could create a participation inequity. This is unavoidable given that the study heavily relies on a phone contact during the recruitment procedures.

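### Protocol sections 2.6, 2.9.1 and 2.11 disagree on whether the primary group-by-time test allows for clustering; if change varies between areas, a plain Wald Z-test rejects too often

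*Protocol*

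**What the plan says.** - **Arms (2.2).** In Ethiopia the intervention arm is in nine woredas and the comparison arm in eight others. In Nigeria the arms are in different LGAs, whose number is not given.
- **Sample size (2.6).** It is based on a "two-sided Wald Z-test using GEE methods, accounting for repeated measures and clustering within groups". The section adds: "Estimates are adjusted by 10% missing/non-response rate and a design effect of 1.2 to account for within community or group clustering".
- **Primary analysis (2.9.1).** Outcomes follow a difference-in-difference design. For the primary binary outcome, the difference in group slopes is tested thus: "The comparison will be made using a Wald Z-test using GEE methods". The only dependence named for this test is AR1 over each subject's two measurements. The section ends with a second model: "Generalized linear mixed affects models will be employed to control for confounding correcting for individual and cluster-level standard errors". How that model relates to the primary test is not stated.
- **Interpretation (2.9.1).** At the follow-ups, and with a qualifier that this holds within reason, "any statistically significant differences between the intervention and comparison groups will be attributed to the intervention".
- **Limitations (2.11).** "The clustering of effects within AGYW from specific facility catchments cannot be controlled".
- **Separate wording difference.** The summary's Methods say "Between group t-tests and chi-square tests of comparison will be conducted to identify secondary outcomes which show statistically significant differences". Section 2.9.1 places the between-group tests at baseline: "Between group t-tests and chi-square tests of comparison will be conducted at recruitment phase".

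**The concern.** The three statements cannot all describe one primary analysis. Section 2.6 has the test allowing for clustering, 2.9.1 writes it with within-girl correlation only, and 2.11 says clustering at the catchment level cannot be handled.

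This matters because every girl in an area is in the same arm. Area differences that stay constant over time cancel in a difference-in-difference, but area differences in change do not. If the girl is the only independent unit, those differences are missing from the standard error: the test rejects too often and the interval is too narrow. Enlarging the sample by 1.2 does not repair this, because it adds girls without changing the variance used in the test. The protocol attaches a causal reading to statistically significant differences, so the choice of standard error bears on the conclusion.

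**Working it through.** **Reproducing the planned figure.** Inputs from 2.6: two-sided 5%, 80% power, 0.30 to 0.40 in the intervention arm, 0.30 to 0.30 in the comparison arm, design effect 1.2, non-response 10%. The within-girl correlation is not in the text shown; 0.5 is assumed.

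- Formula, logit scale: n per arm = (1.960 + 0.842)² × Σ over arms of [1/(p0q0) + 1/(p1q1) − 2ρ/√(p0q0p1q1)] / (log OR)².
- Numbers: 7.849 × (4.474 + 4.762) / 0.4418² = 371.3 per arm, 742.6 in total.
- 742.6 × 1.2 / 0.9 = 990.2, which rounds up to the stated 991. Then 991 × 1.1 = 1,090.

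So the 1.2 enters as a multiplier on sample size. That says nothing about the variance used in the test.

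**Girl-level Z-test.** If the design effect on the change contrast is DE and the standard error omits it, type I error = 2 × [1 − Φ(1.96/√DE)].

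| Assumed DE on change | 1.96/√DE | Type I error |
|---|---|---|
| 1.0 | 1.960 | 5.0% |
| 1.05 | 1.913 | 5.6% |
| 1.1 | 1.869 | 6.2% |
| 1.2 | 1.789 | 7.4% |
| 1.3 | 1.719 | 8.6% |

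At 1.2 the 95% interval has 1/√1.2 = 0.913 of its proper width.

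**Current Ethiopia sample.** Here all of the 1.2 is assigned to woreda-level change, which is an assumption.

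- 991 × 0.9 = 892 girls over 17 woredas is 52.5 each, so the implied ICC of change is 0.2/51.5 = 0.0039.
- 1,330 × 0.9 × 0.9 = 1,077 girls is 63.4 per woreda, so DE = 1 + 62.4 × 0.0039 = 1.24. The formula gives a girl-level type I error of 7.9%.

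Null simulation: 20,000 trials, outcome 0.30, within-girl correlation 0.5 (assumed), woreda SD of change 0.0286, 9 against 8 woredas.

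| Test | Equal woredas | 5-fold size range (assumed) |
|---|---|---|
| Girl-level Z | 7.9% | 8.7% |
| Uncorrected woreda sandwich Z | 8.6% | 9.8% |
| Sandwich × K/(K−2), 15-df t | 4.9% | 6.0% |
| Mancl-DeRouen sandwich, 15-df t | 3.7% | 4.3% |
| Woreda-summary t-test, 15 df | 4.8% | 5.0% |

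A separate run with equal woredas put the uncorrected sandwich Z at 8.1%, so about 8 to 8.6% is a fair statement. Clustering on woreda while keeping the normal reference distribution therefore does not restore 5%.

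**Power, Ethiopia.** At the protocol's 10-point effect, with 1,330 girls and the ICC above, simulated power is about 84% for the woreda-summary t-test or the K/(K−2) sandwich with 15 df. It is about 90% for the uncorrected clustered Z-test.

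**Power, Nigeria.** With DE held at 1.2 and the design non-centrality 1.960 + 0.842 = 2.802, a t-test on clusters minus 2 df gives these results for assumed LGA counts:

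| LGAs | df | Critical t | Power |
|---|---|---|---|
| 4 | 2 | 4.303 | about 35% |
| 8 | 6 | 2.447 | about 65% |
| 12 | 10 | 2.228 | about 71% |

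**The case against.** The strongest reply is that this is loose wording plus detail that belongs in a statistical analysis plan. Section 2.6 says the test allows for clustering. AR1 describes a girl's two measurements and does not exclude an area-level variance. Section 2.9.1 does end with cluster-level standard errors. Cluster unit, sandwich type and degrees of freedom are commonly left to a later plan. Much of this is fair, and the absence of such detail is not the finding. What remains is that the protocol itself fixes the test, its correlation structure and a limitation, and these conflict. It also fixes a Z reference distribution, which is too liberal with 17 areas even on the reading most favourable to the plan.

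Four stronger readings are tempting, and the documents do not support them.

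- *The primary test has a type I error of 7.4%.* That needs both the girl-level reading, which 2.6 points against, and the 1.2 being the design effect on change between woredas, which 2.6 does not say.
- *Section 2.11 admits that area clustering is ignored.* It speaks of facility catchments, which lie below the woreda or LGA.
- *Two models compete to be primary.* Section 2.9.1 ties the primary outcome to the GEE test and gives the mixed model another purpose, confounding. What is missing is a statement that the mixed model is supportive.
- *The standard error alone decides the conclusion.* The attribution sentence is qualified, confounding control follows it, and 2.11 promises triangulation with other data.

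The difference between the summary and 2.9.1 on t-tests and chi-square tests concerns timing and outcomes. It adds no weight to the clustering point.

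**Conclusion.** The inconsistency is certain from the text and should be fixed. Its statistical consequence is conditional: if change varies between areas, a Wald Z-test is too liberal whether it treats the girl as the unit or clusters on 17 woredas without correction.

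The size cannot be fixed from the documents. Girl-level type I error runs from 5.0% (no area variation in change) to 8.6% (design effect 1.3), with 7.4% at 1.2. A larger design effect is not excluded. The simulated figures rest further on the assumed within-girl correlation of 0.5 and on assigning the whole 1.2 to woredas.

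**What to change.** - Reconcile 2.6, 2.9.1 and 2.11 so that they describe one analysis.
- In 2.9.1, name one primary model for the group-by-time term, with variance clustered on the unit that separates the arms (woreda; LGA). Add a small-sample correction that holds when areas differ in size, for example an area-summary t-test or a Mancl-DeRouen sandwich with clusters minus 2 df. State that the mixed model is supportive.
- Use the same variance for between-group comparisons of secondary outcomes. As a separate wording point, align the summary with 2.9.1 on t-tests and chi-square tests.
- In 2.11, say that clustering is handled in the analysis but that the areas are few.
- State the number of LGAs in Nigeria and restate power for that country.

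The cost is wider intervals and some power; no new data are needed for the rewording. In Ethiopia power stays near 84% at the 10-point effect under the assumptions above. The Mancl-DeRouen version costs somewhat more: at a 9.4-point effect it gave 0.738, against 0.782 for the K/(K−2) sandwich. In Nigeria the loss could be severe if LGAs are few, so the count should be known before the correction is adopted there.
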